## **7. Sample Size:**

No similar study was found in the literature. There are three independent groups:

- Video group,
- No visual group,
- Image group.
- Assuming an alpha ( $\alpha$ ) level of 0.05 and a beta ( $\beta$ ) level of 0.20 (power of 80%), and an effect size (Cohen's  $f$ ) of 0.40, it was calculated that approximately 26 participants per group (78 in total) would be required to detect meaningful differences between the three groups.

---

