## **17. Outcome Evaluation:**

The primary endpoint is the tabulation and statistical analysis of STAI responses before and after the procedure among different groups. The secondary endpoint is the writing and publication of the study results.

---

Previous literature has shown that prostate biopsy induces anxiety and depression. Zisman et al., in a prospective study of 211 men, found that 64% experienced decreased well-being and anxiety from the pre-biopsy period up to 30 days after. Fowler et al. showed that anxiety may persist for up to 12 months, even in patients with negative biopsy results. Our study seeks to answer whether pre-procedural videos intensify the anxiety already known to be associated with the biopsy.

---

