### **Name / Signature**

**Principal Investigator:**  
**[name]**

### **Statistical Analysis**

All statistical analyses were performed using SPSS software [insert version]. Continuous variables were expressed as mean  $\pm$  standard deviation, and categorical data as frequencies and percentages. Group comparisons were made using the Kruskal-Wallis test for non-parametric data and ANOVA for normally distributed data. Post-hoc pairwise comparisons were conducted using the Mann-Whitney U test with Bonferroni correction. A p-value  $<0.05$  was considered statistically significant. A priori power analysis was conducted using G\*Power

software version 3.1.9.7 to determine the adequate sample size. Assuming an alpha ( $\alpha$ ) level of 0.05 and a beta ( $\beta$ ) level of 0.20 (power of 80%), and an effect size (Cohen's  $f$ ) of 0.40, it was calculated that approximately 26 participants per group (78 in total) would be required to detect meaningful differences between the three groups.

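### The stated 80% power belongs to a three-group omnibus test: it does not give the power for video versus verbal-only information, and it does not match the stated 78 patients

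*Combined protocol and SAP*

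**What the plan says.** Section 7 describes the design with "There are three independent groups" (video, no visual, image) and states that "it was calculated that approximately 26 participants per group (78 in total) would be required to detect meaningful differences between the three groups", at alpha 0.05, beta 0.20 and Cohen's f = 0.40. It gives no means, no SD and no pattern of means. The closing Statistical Analysis section repeats the calculation and attributes it to G*Power, without naming the test family.

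For the analysis, that section says "Group comparisons were made using the Kruskal-Wallis test for non-parametric data and ANOVA for normally distributed data". Pairwise comparisons follow as post-hoc Mann-Whitney tests with a Bonferroni correction; the number of comparisons is not given.

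The question is worded around video. The title and the aim in Section 2 concern the effect of videos, and Section 17 says "Our study seeks to answer whether pre-procedural videos intensify the anxiety already known to be associated with the biopsy". Section 4 labels the verbal-only arm as the control group. The primary endpoint in Section 17, however, is STAI before and after the procedure compared across the groups, and no section singles out a pair.

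**The concern.** Cohen's f measures how far the three group means spread around their average. The same f can come from a large video effect, a modest one or none, so the quoted 80% has no definite meaning for the question in Section 17.

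Two things are at stake. A null video result could be read against a power figure that was never calculated for it. And because no contrast is named in advance, the comparison closest to the study's question is tested only post hoc, with a multiplicity penalty that a single prespecified contrast would not carry.

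Separately, the three inputs and the 78 patients do not agree, so the 80% is not the omnibus power of the stated design either.

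**Working it through.** **Inputs from the documents.** Alpha: "level of 0.05 and a beta". Power and effect size: "level of 0.20 (power of 80%), and an effect size" "of 0.40, it was calculated that approximately 26 participants per group". Three groups, 78 in total.

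**Assumptions added here.** Normal data, equal SDs, 26 evaluable per group, two-sided tests, and three pairs in the Bonferroni correction (0.05/3 = 0.0167).

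**Step 1: the plan's own figure.** One-way ANOVA, noncentral F with df = (2, N − 3) and noncentrality λ = N·f² = 0.16·N.

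| N (per group) | λ | Power |
|---|---|---|
| 63 (21) | 10.08 | 79.8% |
| 66 (22) | 10.56 | 81.8% |
| 78 (26) | 12.48 | 88.3% |

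So 80% power needs 22 per group. With 78 patients, 80% power is reached at f = 0.36. Several unstated choices would lead to about 26 per group: a 15% loss allowance (66/0.85 = 77.6), alpha 0.025, or a worst-case rank-test efficiency (22/0.864 = 25.5). The documents mention none of them.

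**Step 2: what f = 0.40 implies for video minus verbal-only.** With f² = (1/3)·Σ(μᵢ − μ̄)²/σ² and d the difference in SD units:

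- Evenly spaced means, range D: f = D/√6, so D = 0.40 × 2.449 = 0.98. This is the largest difference between any two groups that f = 0.40 allows.
- Adjacent groups in that pattern: d = 0.98/2 = 0.49.
- One group differing from two equal ones: f = d·√2/3, so d = 3 × 0.40/1.414 = 0.85.
- Only the drawings group differing: d = 0 between video and verbal-only.

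**Step 3: power for video versus verbal-only at 26 per group.** Mann-Whitney by simulation; t-test by noncentral t.

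| Pattern | d | Mann-Whitney, 0.05/3 | t-test, 0.05/3 | Mann-Whitney, 0.05 | t-test, 0.05 |
|---|---|---|---|---|---|
| The two are the extremes | 0.98 | 82% | 85% | 92% | 93% |
| Video or verbal-only alone differs | 0.85 | 69% | 72% | 83% | 85% |
| Adjacent, evenly spaced | 0.49 | 23% | 25% | 39% | 41% |

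The Mann-Whitney figures at 0.05/3 move by up to about one percentage point between simulation runs and with the continuity correction (for example 68% to 69% in the second row).

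Omnibus power is about 88% in every pattern, including the one where only drawings differ. There the corrected video versus verbal-only test is significant in about 1.6% of trials, which is its false-positive rate.

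**Step 4: detectable difference for one contrast.** At 26 per group, two-sided 0.05 and 80% power, d is about 0.79 for a t-test and about 0.82 for Mann-Whitney.

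**The case against.** The strongest reply is that the plan is internally consistent. The endpoint, the sample size and the main test all compare three groups, Section 4 defines three parallel arms, and no comparator is named for the video question. Section 7 claims power for differences among three groups and nothing pairwise. That stands: video versus verbal-only as the main contrast is inferred from the title, the aim, Section 17 and the control label, and making the image arm secondary is a design choice.

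A reader might go further and infer any of the following, which the documents do not support:

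- *A significant omnibus test would be credited to the video.* The planned corrected pairwise tests give video versus verbal-only its own test, and when only drawings differ they wrongly favour a video difference only about 1.6% of the time.
- *Power for the video question can fall to nothing.* Where video and verbal-only have the same mean there is no effect to miss, so that case is not lost power.
- *82% is the most the trial can offer.* That ceiling belongs to Mann-Whitney at an assumed 0.05/3. A single contrast at 0.05 reaches 92% to 93%, and 83% to 85% if video alone differs.
- *The omnibus step itself costs power.* Requiring it first lowered pairwise power by less than one percentage point in every pattern.
- *The trial is too small for its stated target.* At f = 0.40 it is larger than the omnibus test needs.

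**Conclusion.** The point holds in a limited form. The 80% is an omnibus figure that leaves power for video versus verbal-only undetermined: about 82%, 69% or 23% for the three patterns with a true difference under the planned post-hoc step, and about 92%, 83% and 39% if the same Mann-Whitney test were the single contrast at two-sided 0.05. The omnibus figure is also misstated for 78 patients (88%, with 66 sufficient for 80%).

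The planned analysis is valid, and its pairwise correction guards against false credit to video. What is missing is a named contrast and a power statement that belongs to it. The pairwise percentages rest on normal data, equal SDs, three Bonferroni pairs and 26 evaluable per group. The last is optimistic, because Section 10 foresees withdrawals and exclusion during biopsy and no loss allowance is stated.

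**What to change.** In Sections 7 and 17 and the closing Statistical Analysis section:

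1. Name video versus verbal-only on STAI-I as the primary contrast. State one time point or measure (pre-procedure, post-procedure or change) and one test, at two-sided 0.05.
2. Make the image-group comparisons secondary, with Bonferroni correction.
3. State that 26 evaluable per group gives 80% power for a difference of about 0.79 SD (t-test or linear model) or about 0.82 SD (Mann-Whitney), whichever test is chosen.
4. State that f = 0.40 with 78 patients gives 88% omnibus power, or give the unstated allowance that led from 66 to 78. Do not present 80% as the power for the video question.
5. If outcome data have already been seen, label the contrast as post hoc. The documents do not settle this, but Section 14 ends recruitment on 30.12.2024 and the closing section is written in the past tense.

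If the investigators want all three comparisons to be co-primary, the plan should say so and give the pairwise power.

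The cost is wording in three places and no extra patients. The downside is that the image-group comparisons become secondary.

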## **8. Inclusion Criteria:**

- Male patients aged 50–80
- Biopsy planned due to elevated PSA
- Voluntary participation

---

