#### **Video Group:**

Patients are given verbal information. Then:

- VAS test is applied.
- Videos about the procedure are found and watched with the patients via digital video platforms.
- STAI-II and STAI-I are administered pre-procedure.
- After biopsy: VAS and STAI-I are re-administered.

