#### **5. Target Volunteer Group:**

Adult males with elevated PSA levels and planned biopsy.

---

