## **9. Exclusion Criteria:**

- Organic mental disorders, dementia, depressive and anxiety disorders, PTSD, acute psychotic or bipolar disorders
- Patients with cognitive or physical impairments that prevent informed consent (e.g., blindness, moderate to severe mental retardation)
- Panic disorder diagnosis
- Patients with pre-procedure VAS  $\geq 5$ , suggestive of significant anxiety-stress disorders

---

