## **11. Parameters to be Measured:**

- Age
- PSA levels
- Subjective findings of rectal examination
- Post-procedure complications
- Anxiety and stress scores (STAI-I and II, pre-op and post-op)
- Pain scores (VAS)

---

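### Previous prostate biopsy is neither an eligibility criterion nor a recorded item, so an imbalance between the groups could bias the STAI comparison in either direction without being seen or corrected

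*Combined protocol and SAP*

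**What the plan says.** All references are to the combined protocol and SAP.

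- **Who may enter.** Section 5 describes the target group as "Adult males with elevated PSA levels and planned biopsy". Section 8 adds an age range of 50 to 80, consent, and "Biopsy planned due to elevated PSA". None of these separates a first biopsy from a repeat.
- **Who is excluded.** The nearest exclusion in Section 9 is diagnostic: "Organic mental disorders, dementia, depressive and anxiety disorders, PTSD, acute psychotic or bipolar disorders". The section also excludes panic disorder, impairments that prevent consent, and a VAS of 5 or more before the procedure. A previous biopsy is not mentioned.
- **What is recorded.** Section 11 lists age, PSA, "Subjective findings of rectal examination", "Post-procedure complications", STAI and VAS. Biopsy history is not on the list.
- **What is compared.** Section 17: "The primary endpoint is the tabulation and statistical analysis of STAI responses before and after the procedure among different groups". The closing Statistical Analysis text uses ANOVA or Kruskal-Wallis and names no covariate. Section 18 lists linear regression but specifies no model.
- **Why history could matter.** Section 17 also reports that "anxiety may persist for up to 12 months, even in patients with negative biopsy results".
- **Order of events.** Under Video Group, the step "Videos about the procedure are found and watched with the patients via digital video platforms" comes before the first STAI. The Image Group has the same order, with drawings instead. Section 4 describes no random allocation.

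**The concern.** A man with an earlier negative biopsy and a PSA that is still raised meets every criterion. By the protocol's own account he may still carry anxiety from that procedure, and anxiety is the primary outcome. If such men are more common in one group, part of any STAI difference between groups would reflect their history rather than the video or drawings.

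Two usual safeguards are missing. Without randomisation, balance on history cannot be presumed even on average. And because STAI-I is first taken after the material in two of the three groups, no state-anxiety score from before the education exists to show that the groups started alike. As the history itself is not collected, the problem could not be examined afterwards from the study data.

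There is a smaller related gap. Recruitment in Section 14 runs from 10.12.2023 to 30.12.2024, which is 386 days, and nothing says that a man re-biopsied in that time may enter only once.

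**Working it through.** **Inputs from the plan** (Section 7 and the closing Statistical Analysis text): three groups, Cohen's f = 0.40, alpha 0.05, power 80%, 26 per group, N = 78.

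**Inputs assumed here**, because the documents give none: q, the share of repeat-biopsy men (10-30%); s, their shift in anxiety in SD units (0.5 or 1.0); r, the fraction of the education effect that they retain.

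**1. The plan's own figure.** One-way ANOVA F-test, noncentral F with λ = N·f². At N = 78, λ = 78 × 0.16 = 12.48 and power is 0.883. The same test needs only 22 per group (N = 66, power 0.818), so 26 per group is not reproduced as worded. That is a separate matter; 0.883 is simply the reference value below.

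**2. Imbalance, the mechanism that matters here.** For two groups of 26 drawn from the same population, the difference in repeat share has SD √[2q(1−q)/26]. Multiplying by s gives the SD of the spurious difference in mean anxiety.

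| q | SD of difference in share | 95% range (±1.96 SD) | Spurious difference at s = 0.5 (SD) |
|---|---|---|---|
| 10% | 0.083 | ±16 points | 0.042 SD units |
| 20% | 0.111 | ±22 points | 0.055 SD units |
| 30% | 0.127 | ±25 points | 0.064 SD units |

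For example, at q = 20%: √(2 × 0.2 × 0.8 / 26) = 0.111, and 0.5 × 0.111 = 0.055. These are chance figures. If allocation is not random, the imbalance may be larger, and no bound can be derived from the documents. The sign may go either way.

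**3. Carry-over shared equally by the groups.** A shift common to all groups leaves the raw group difference unchanged and only adds variance: f_eff = 0.40 / √[1 + q(1−q)s²].

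| q | Power at N = 78, s = 0.5 | Power at N = 78, s = 1.0 |
|---|---|---|
| 10% | 0.875 | 0.853 |
| 20% | 0.869 | 0.829 |
| 30% | 0.865 | 0.812 |

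Power stays above the planned 80% throughout.

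**4. Reduced response in repeat men.** With s = 0, f_eff = 0.40 × [1 − q(1−r)].

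| q | Power, half the effect (r = 0.5) | Power, assumed no response (r = 0) |
|---|---|---|
| 10% | 0.846 | 0.803 |
| 20% | 0.803 | 0.698 |
| 30% | 0.754 | 0.574 |

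The right-hand column is an assumed no-response scenario. Nothing in the documents supports r = 0, or any r below 1.

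**5. Analysing first-biopsy men only, out of 78 enrolled.** At q = 10%, 78 × 0.9 ≈ 70 men remain and power at f = 0.40 is 0.842. At q = 30%, 78 × 0.7 ≈ 55 remain and power is 0.735. Under carry-over alone this is worse than keeping everyone (0.853 and 0.812 even at s = 1.0).

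**The case against.** The strongest reply is that Section 5 deliberately describes a broad population, and repeat-biopsy men legitimately belong to it. Section 9 already removes men with diagnosed anxiety disorders or a high VAS before the procedure, which may take out some of those with the strongest carry-over. STAI-II is collected in every group and may absorb some of the rest. The chance imbalance in the table is also small beside a planned effect of f = 0.40.

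Much of this stands. Eligibility of repeat men is not in itself an error, and the illustrated bias is modest if allocation behaves like a random draw. But the exclusions concern diagnoses and VAS, not biopsy history. No adjustment for STAI-II is planned, and in the video and image groups it too is listed after the material. And no random allocation is described, so the chance figures are not an upper limit.

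A reader might also infer that repeat-biopsy men dilute the education effect and leave the study underpowered. The documents do not support that. Carry-over shared by the groups does not shrink the difference, and power holds above 80% in the scenarios shown. Dilution requires that men who know the procedure respond less to the material. The protocol never says so, and a video might affect them more, less or in the opposite direction. Nor does anything indicate that double enrolment is expected; the plan only fails to rule it out, while Section 7 treats the groups as independent.

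**Conclusion.** The concern holds as a gap in measurement and confounding control. The protocol cites evidence that biopsy has a lasting influence on anxiety, its primary outcome, then neither restricts on biopsy history, records it nor adjusts for it, in a comparison with no described randomisation and, in two groups, no STAI taken before the education.

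The bias is of unknown size and direction. The one figure offered, a spurious difference with an SD of about 0.04 to 0.06 SD units, rests on assumed repeat shares of 10-30%, an assumed 0.5 SD shift, and imbalance no worse than chance. A loss of power is not established; figures as low as 57% belong only to the assumed scenario of a 30% repeat share with no response in those men. This is an inexpensive improvement that should be made, not a flaw that invalidates the study.

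**What to change.** - **Section 11:** add previous prostate biopsy (yes/no, date, result), taken from the hospital record. For men already enrolled it can be filled in retrospectively.
- **Section 18 and the closing Statistical Analysis text:** report previous biopsy by group. Include it (yes/no) as a covariate in the STAI group comparison, for example through the linear regression that Section 18 already lists, since Kruskal-Wallis cannot carry a covariate. Add a sensitivity analysis in first-biopsy men.
- **Section 8:** state that each man is enrolled once only.

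The cost is one chart item and one degree of freedom. The latter is negligible at N = 78: residual degrees of freedom fall from 75 to 74 and power at f = 0.40 stays at 0.883.

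Restricting enrolment to first biopsies is optional. It removes the problem outright but narrows the population, and reaching 78 would mean assessing about 87, 98 or 112 otherwise eligible men at an assumed repeat share of 10%, 20% or 30% (78 divided by 0.9, 0.8 or 0.7). Making first-biopsy men the primary analysis after enrolment has the power cost shown in step 5, so it is better kept as a sensitivity analysis. Any power figure quoted for reduced response should be labelled as an assumed scenario.

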## **9. Exclusion Criteria:**

- Organic mental disorders, dementia, depressive and anxiety disorders, PTSD, acute psychotic or bipolar disorders
- Patients with cognitive or physical impairments that prevent informed consent (e.g., blindness, moderate to severe mental retardation)
- Panic disorder diagnosis
- Patients with pre-procedure VAS  $\geq 5$ , suggestive of significant anxiety-stress disorders

---

## **10. Withdrawal Criteria:**

- Participants may withdraw at any time.
- Patients who become excessively anxious or restless during biopsy will have the procedure rescheduled under general anesthesia and be excluded from the study.

---

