**3. Expected Benefits and Risks:**

If an increase in patients' anxiety and stress scores is observed, it may highlight the need for additional measures to inform patients prior to procedures. Videos could be adjusted to reduce stress, potentially making the biopsy experience more comfortable. However, patients who become overly anxious after watching such videos might delay or avoid diagnosis and treatment, as seen in psychiatric consultations. This study may also guide how digital content should be curated.

---

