#### **Image Group:**

Patients are given verbal information. Then:

- VAS test is applied.
- Illustrated drawings (from books) about the procedure are shown to the patients.
- STAI-II and STAI-I are administered pre-procedure.
- After biopsy: VAS and STAI-I are re-administered.

---

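### Men excluded for anxiety or restlessness during biopsy leave the study after the education has acted, so the STAI-I comparison (and possibly VAS) can be biased between groups

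*Combined protocol and SAP*

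**What the plan says.** Section 10 (Withdrawal Criteria) states: "Patients who become excessively anxious or restless during biopsy will have the procedure rescheduled under general anesthesia and be excluded from the study". It gives no threshold or scale for the trigger.

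Section 4 fixes the order of events. After verbal information and a first VAS, the video group watches procedure videos; in the image group, "Illustrated drawings (from books) about the procedure are shown to the patients". Only then, in the video group's schedule, "STAI-II and STAI-I are administered pre-procedure", and the image group follows the same order. STAI-I and VAS are repeated after the biopsy.

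Section 17 defines the endpoint: "The primary endpoint is the tabulation and statistical analysis of STAI responses before and after the procedure among different groups". It names no single time point. It also states the question: "Our study seeks to answer whether pre-procedural videos intensify the anxiety already known to be associated with the biopsy".

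Section 11 lists "Anxiety and stress scores (STAI-I and II, pre-op and post-op") together with VAS and complications, but no count of biopsies stopped for anxiety or restlessness. Section 18 and the closing Statistical Analysis text name the tests. They define no analysis population, missing-data method or sensitivity analysis.

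**The concern.** The exclusion acts after the groups have been treated differently, and it selects on something close to what is being measured. If the video makes men more anxious, more of them may reach the trigger, and the most anxious would leave the video group in greater numbers than the control group. The men who remain would then look more alike across groups than the men who entered. A finding of no STAI difference could not be told apart from the removal of the most affected patients.

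Restlessness may also reflect pain, so the post-procedure VAS comparison is open to the same selection.

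Two useful pieces of information are at risk without need. One is the pre-procedure STAI-I, which was collected after the education and before the trigger, so the selection cannot distort it if everyone is kept. The other is the number of stopped biopsies in each group, which bears directly on the study question.

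**Working it through.** **The plan's own figure.** Section 7 says that "approximately 26 participants per group (78 in total) would be required to detect meaningful differences between the three groups", with alpha 0.05, power 80% and Cohen's f = 0.40. For a one-way ANOVA F test the noncentrality is f²N, with 2 and N − 3 degrees of freedom.

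- N = 66: 0.16 × 66 = 10.56, power 81.8%. This is the smallest equal-group size above 80%; N = 63 gives 79.8%.
- N = 78: 0.16 × 78 = 12.48, power 88.3%.

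The stated 78 is therefore more than its stated inputs require. The present point does not depend on that, but 88.3% is the benchmark for a trial with no exclusions.

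**Inputs taken from the plan.** 26 per group, f = 0.40, alpha 0.05. If only the video group differs, the means are 0, 0, d and f = d√2/3, so d = 0.40 × 3/√2 = 0.8485 SD.

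**Inputs assumed, because the documents give none.**
- Control (and image) exclusion p_c: 1%, 2% or 5%.
- Correlation ρ between the trigger and STAI-I: 0.3, 0.5 or 0.7.
- Shift s of the trigger in the video group: ρd, or the full d.
- Groups otherwise comparable.

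**Model.** The trigger is normal with mean s and SD 1, and a man is kept if it stays below t = z(1 − p_c). With b = t − s and λ = φ(b)/Φ(b):
- proportion excluded = 1 − Φ(b)
- retained STAI-I mean = true mean − ρλ
- retained variance = 1 − ρ²(bλ + λ²)
- observed difference = d − ρ(λ_video − λ_control)

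Power uses the noncentral F with the retained means, variances and group sizes.

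**One cell in full** (p_c = 5%, ρ = 0.7, s = d). t = 1.645 and b = 1.645 − 0.849 = 0.796. λ_control = 0.109 and λ_video = 0.369. Video exclusion is 21%, or 5.5 of 26. The difference is 0.8485 − 0.7 × (0.369 − 0.109) = 0.8485 − 0.182 = 0.67 SD. Attenuation is 0.182/0.8485 = 21%. Power is 66%, and a simulation of 6,000 trials at the same values also gave 66%.

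**All cells**, for p_c = 1% / 2% / 5%:

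| ρ | Trigger shift | Video excluded (%) | Attenuation (%) | Power (%) |
|---|---|---|---|---|
| 0.3 | ρd | 2 / 4 / 8 | 1 / 1 / 2 | 87 / 87 / 85 |
| 0.3 | d | 7 / 11 / 21 | 4 / 6 / 9 | 84 / 81 / 74 |
| 0.5 | ρd | 3 / 5 / 11 | 2 / 4 / 6 | 87 / 85 / 82 |
| 0.5 | d | 7 / 11 / 21 | 7 / 10 / 15 | 82 / 78 / 70 |
| 0.7 | ρd | 4 / 7 / 15 | 5 / 8 / 13 | 85 / 83 / 77 |
| 0.7 | d | 7 / 11 / 21 | 10 / 14 / 21 | 81 / 76 / 66 |

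In 12 of the 18 cells power stays above the planned 80%, helped by the surplus in the sample size. If the trigger does not move (s = 0), λ is the same in every group and attenuation is zero.

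**Other directions.**
- *Trigger moves, STAI-I does not.* At ρ = 0.5, p_c = 5%, s = d, a false difference of −0.5 × (0.369 − 0.109) = −0.13 SD appears. The ANOVA rejects in 6.9% of trials instead of 5%.
- *Change score.* The bias is −(ρ_post − ρ_pre)(λ_video − λ_control). With correlations of 0.3 and 0.7, p_c = 5% and s = d, this is 0.4 × 0.26 = 0.10 SD. Its sign depends on which time point correlates more strongly with the trigger, and it is zero if the two are equal.

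**The case against.** **The event may be rare.** Section 9 already removes anxiety disorders, panic disorder, PTSD and men with a pre-procedure VAS of 5 or more. The documents give no rate, and at the low end of the table the loss is trivial. This stands, and it is why no single size can be given.

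**A comparable post-procedure score cannot be obtained once the biopsy is rescheduled.** This also stands. That loss is unavoidable; the other two are not.

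**The exclusion may mean only the end of further participation.** Section 10 is headed as withdrawal, and no section says that collected data are discarded. The plain reading is that the patient leaves the study with his data, but the text is not explicit. That is itself a reason to settle it.

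**Stronger readings that the documents do not support.**
- A reader might infer that the rule certainly hides a video effect. It does not: without an effect on STAI or the trigger there is no bias, and for change scores the direction is not fixed.
- A reader might push the correlation to 1 and report attenuation near 31% with power of 62%. Nothing in the documents supports so tight a link, least of all for a trigger that includes restlessness.
- A reader might say that the plan removes exactly the patients whom Section 3 worries about. Section 3 says that "patients who become overly anxious after watching such videos might delay or avoid diagnosis and treatment". That concerns putting off diagnosis and treatment, not distress during a biopsy already under way.

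**Comparability of the groups.** The model takes the groups as otherwise comparable, but Section 4 states no allocation method. Pre-existing differences could outweigh the loss of a few men per group.

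**Conclusion.** The concern holds as a possibility that the plan leaves open. The exclusion follows the group-specific education, its trigger is related to the primary endpoint, and nothing in the analysis sections offsets it. When STAI-I and the trigger move in the same direction, a single-time-point difference is most likely pulled toward no difference.

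Under the assumed values, attenuation is about 1% to 21% and power about 87% to 66%, against 88% with 78 complete patients. That is negligible to material, and the documents cannot say where in the range the trial lies. The mechanism is clear from the text; the size rests wholly on the assumed exclusion rate, correlation and trigger shift. This should be fixed because the remedy is cheap, not because a large bias has been shown.

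**What to change.** Leave the clinical rescheduling rule as it is and change only the handling of data.

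- **Section 10.** Replace the closing clause on exclusion with a statement that these patients, unless they withdraw consent, stay in the analysis in their group.
- **Section 11.** Add the number of biopsies stopped for anxiety or restlessness.
- **Section 18.** (1) Their pre-procedure STAI-I enters the group comparison at that time point. (2) Stopped biopsies are reported by group as a count with a confidence interval. (3) Their post-procedure STAI-I and VAS are treated as missing, and post-procedure and change-score comparisons are labelled as restricted to patients who completed the biopsy.

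The count should stay descriptive: with 26 against 26, Fisher's exact test has only 26% power even for 5% against 21%. A worst-rank analysis of post-procedure STAI-I is optional, and as a sensitivity analysis only. It scores restless men as the most anxious, and in simulation it rejected in 5–9% of trials when only the trigger moved.

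The cost is a few sentences, one extra tally, and a post-procedure result stated more cautiously.
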